### **5.4. HANDLING OF MISSING DATA**

#### **5.4.1. Observed Cases (OC)**

No imputation is done of missing values.

#### **5.4.1. Last Observation Carried Forward (LOCF)**

A missing W4 analysis visit will be imputed by the last preceding non-missing data point. This can be a baseline value.

A missing W12 analysis visit will be imputed by the last preceding non-missing data point. Again this could be a baseline value. This will only be done for the main descriptive statistics and comparisons vs placebo. Correlation analyses will be performed on OC only.

#### **5.4.2. Handling of Missing Date(Time) or Partially Known Date(Time)**

No imputation will be done of missing date(time) fields, nor of the missing parts of partially known date(time) fields. When needed, a worst-case selection will be made.

### **5.5. HANDLING OF OUTLIERS**

All measured values will be included in the analyses. However, analyses may be repeated after exclusion of outliers.

### **5.6. STRATIFICATION FACTORS**

In case there is a discrepancy in randomization stratification stratum between IWRS and the actual eCRF data, then the actual eCRF stratum will be used in analyses and analysis models.

These are available in the final ADaM.ADSL dataset: region and previous use of biologics.

## **6. SOFTWARE AND PROCEDURES**

### **6.1. SOFTWARE**

SAS version 9.2 will be used for programming.

Each TLF will be presented in a separate PDF file. Image files (e.g. PNG or in Excel) should be available for plots.

SAS line size and page size:

- SAS LSIZE = 144
- SAS PSIZE = 48

Page layout:

- landscape
- paper size: A4
- margins in MS Word:
  - top, bottom, left, right: 2.5 cm
  - gutter: 0 cm
  - header, footer, from edge: 1.3 cm

### **6.2. PROCEDURES**

Analyses will comply with ICH regulations, in particular: (ICH-E3) , (ICH-E6) and (ICH-E9).

The following Galapagos SOPs will be followed:

- SOP-CLI-001: Developing Clinical Study Documents (version 1.0)
- SOP-CLI-003: Managing Data Processing Activities (version 1.0)

The following [REDACTED] STAT SOPs will be followed:

- [REDACTED]-SOP-ST-003\_1\_0: Statistical Analysis (Date effective: 30 September 2015)
- [REDACTED]-SOP-ST-004\_1\_0: SAS Programming for Statistical Analysis (Date effective: 30 September 2015)

### **6.3. FORMATS**

Derived data will be following CDISC ADaM 2.1 format. Since this extra analysis only contains PD, only one derived ADaM dataset ADPD2 will be created, containing the new PD parameters. A “DEFINE” file is not needed.

## **7. STATISTICAL METHODS**

### **7.1. PLANNED ANALYSES, PROTOCOL AMENDMENTS INCLUDED**

A descriptive analysis will present the actual values, changes from baseline and percent changes from baseline.

Treatment arms will be compared (similarly to efficacy) via an ANCOVA model on the changes from baseline, with explanatory factors: treatment, baseline value, stratification factors (geographical region, previous use of biologics). Pairwise comparisons versus placebo will be presented, corrected for multiplicity using Hommel’s method. Exploratory comparisons between the two regimens within each dose level will be presented as well.

Correlations versus efficacy and safety parameters will be investigated via logistic regression or ANCOVA models.

Figures will be added to depict the data.

Early dropouts and missing analysis visits will be imputed via the LOCF algorithm for the descriptive analysis and comparisons vs placebo. Correlation analyses will be performed on OC only.

### **7.2. CHANGES TO THE PLANNED ANALYSES, NOT COVERED BY PROTOCOL AMENDMENTS**

Not applicable – all these analyses are post-lock.

## **8. DEFINITIONS OF PHARMACODYNAMICS ANALYSIS TABLES, LISTINGS AND FIGURES**

All analyses will be run on the PD population, unless specified otherwise.

### 8.1. PD PARAMETERS

The raw PD markers will be provided by the bioanalysis lab: GM-CSF, IFN $\gamma$ , IL-1 $\beta$ , IL-2, IL-4, IL-5, IL-6, IL-7, IL-8, IL-10, IL-12 (p70), IL-13, IL-17A, IL-21, IL-23, MIP-1 $\alpha$ , MIP-1 $\beta$  and TNF- $\alpha$ . All results are expressed in pg/mL. The raw values (with their unit) will be used in the analysis without any transformation or manipulation (except for the imputation of values BLOQ or missing values).

Analysis will show actual values, changes from baseline and percent changes from baseline.

%change from baseline = 100 x (change from baseline) / baseline, and is only defined when the baseline  $\neq$  0.

### 8.2. STEP 1: OVERALL ANALYSIS OF THE BIOMARKERS

**Table PD 1: Descriptive statistics of the actual values**

Descriptive statistics of the actual values per time point, and per treatment group.

The table will show:

- LOCF
- observed-case

Mock:

		GLPG0634 q.d. dose groups			GLPG0634 b.i.d. dose groups	
Week	Statistic	Placebo (N=XXX)	100 mg q.d. (N=XXX)	200 mg q.d. (N=XXX)	50 mg b.i.d. (N=XXX)	100 mg b.i.d. (N=XXX)
Baseline						
	N	XXX	XXX	XXX	XXX	XXX
	N_det[1]	XXX	XXX	XXX	XXX	XXX
	Mean	XX.X	XX.X	XX.X	XX.X	XX.X
	SE	XX.XX	XX.XX	XX.XX	XX.XX	XX.XX
	SD	XX.XX	XX.XX	XX.XX	XX.XX	XX.XX
	Median	XX.X	XX.X	XX.X	XX.X	XX.X
	Min,Max	XX,XX	XX,XX	XX,XX	XX,XX	XX,XX
	GeoMean	XX.X	XX.X	XX.X	XX.X	XX.X
Week 4 LOCF						
	N	XXX	XXX	XXX	XXX	XXX
	N_det[1]	XXX	XXX	XXX	XXX	XXX
	Mean	XX.X	XX.X	XX.X	XX.X	XX.X
	SE	XX.XX	XX.XX	XX.XX	XX.XX	XX.XX
	SD	XX.XX	XX.XX	XX.XX	XX.XX	XX.XX
	Median	XX.X	XX.X	XX.X	XX.X	XX.X
	Min,Max	XX,XX	XX,XX	XX,XX	XX,XX	XX,XX
	GeoMean	XX.X	XX.X	XX.X	XX.X	XX.X
Week 12 LOCF						
	N	XXX	XXX	XXX	XXX	XXX
	N_det[1]	XXX	XXX	XXX	XXX	XXX
	Mean	XX.X	XX.X	XX.X	XX.X	XX.X
	SE	XX.XX	XX.XX	XX.XX	XX.XX	XX.XX
	SD	XX.XX	XX.XX	XX.XX	XX.XX	XX.XX
	Median	XX.X	XX.X	XX.X	XX.X	XX.X
	Min,Max	XX,XX	XX,XX	XX,XX	XX,XX	XX,XX
	GeoMean	XX.X	XX.X	XX.X	XX.X	XX.X

[1] Number of results >LLOQ and <ULOQ.

Note that this table contains geometric means, but none of the other tables need to.

**Table PD 2: Descriptive statistics of the changes from baseline**

Descriptive statistics of the changes from baseline per time point, and per treatment group.

The table will show:

- LOCF
- observed-case

Mock:

GLPG0634-CL-203 (DARWIN1) SAS date and time  
Page X of Y

Table PD 2: Descriptive statistics of the changes from baseline

---

Add-on therapy to methotrexate. Population: PD. Imputation method: LOCF (last observation carried forward)  
Parameter: PD marker (pg/mL)

---

Week	Statistic	Placebo (N=XXX)	GLPG0634 q.d. dose groups		GLPG0634 b.i.d. dose groups	
			100 mg q.d. (N=XXX)	200 mg q.d. (N=XXX)	50 mg b.i.d. (N=XXX)	100 mg b.i.d. (N=XXX)
Week 4 LOCF						
	N	XXX	XXX	XXX	XXX	XXX
	Mean	XX.X	XX.X	XX.X	XX.X	XX.X
	SE	XX.XX	XX.XX	XX.XX	XX.XX	XX.XX
	SD	XX.XX	XX.XX	XX.XX	XX.XX	XX.XX
	Median	XX.X	XX.X	XX.X	XX.X	XX.X
	Min,Max	XX,XX	XX,XX	XX,XX	XX,XX	XX,XX
Week 12 LOCF						
	N	XXX	XXX	XXX	XXX	XXX
	Mean	XX.X	XX.X	XX.X	XX.X	XX.X
	SE	XX.XX	XX.XX	XX.XX	XX.XX	XX.XX
	SD	XX.XX	XX.XX	XX.XX	XX.XX	XX.XX
	Median	XX.X	XX.X	XX.X	XX.X	XX.X
	Min,Max	XX,XX	XX,XX	XX,XX	XX,XX	XX,XX

**Table PD 3: Descriptive statistics of the percent changes from baseline**

Repeat table for the percent changes from baseline.

**Table PD 4: Summary with overall p-value and pairwise comparisons versus placebo**

ANCOVA model on the LOCF change from baseline biomarker at each time point. Factors in the model are: treatment, baseline value of the PD marker, region, and previous use of biologics.

Per time point, the table will present:

- Overall type-III p-value for all explanatory factors in the model.
- Per group: difference in LS-means versus the placebo group (GLPG0634 minus placebo), together with a 95% confidence interval of this difference.
- Per group: p-value for pairwise comparison versus the placebo group, derived from contrasts within the overall model. These p-values will be presented both as uncorrected p-values as well as corrected for multiplicity according to Hommel’s closed-testing method (SAS PROC MULTTEST).

Mock:

GLPG0634-CL-203 (DARWIN1)

SAS date and time  
Page X of Y

Table PD 4: Summary with overall p-value and pairwise comparisons versus placebo (LOCF)

Add-on therapy to methotrexate. Population: PD. Imputation method: LOCF (last observation carried forward)  
Parameter: PD marker (pg/mL)

Week and statistic	Overall	GLPG0634 q.d. dose groups		GLPG0634 b.i.d. dose groups		
		Placebo (N=XXX)	100 mg q.d. (N=XXX)	200 mg q.d. (N=XXX)	50 mg b.i.d. (N=XXX)	100 mg b.i.d. (N=XXX)
Week 4 LOCF						
Overall p-values: [1]						
- Treatment	X.XXXX					
- Baseline value	X.XXXX					
- Region	X.XXXX					
- Prior biologics	X.XXXX					
Pairwise comparisons versus Placebo: [2]						
- Sample mean (SE)		XX.X (XX.XX)	XX.X (XX.XX)	XX.X (XX.XX)	XX.X (XX.XX)	XX.X (XX.XX)
- LS-mean (SE)		XX.X (XX.XX)	XX.X (XX.XX)	XX.X (XX.XX)	XX.X (XX.XX)	XX.X (XX.XX)
- LS-mean difference (SE)			XX.X (XX.XX)	XX.X (XX.XX)	XX.X (XX.XX)	XX.X (XX.XX)
- 95% CI of the difference			XXX.X, XXX.X	XXX.X, XXX.X	XXX.X, XXX.X	XXX.X, XXX.X
- Uncorrected p-value			X.XXXX	X.XXXX	X.XXXX	X.XXXX
- Corrected p-value			X.XXXX	X.XXXX	X.XXXX	X.XXXX
Week 12 LOCF						
Overall p-values: [1]						
- Treatment	X.XXXX					
- Baseline value	X.XXXX					
- Region	X.XXXX					
- Prior biologics	X.XXXX					
Pairwise comparisons versus Placebo: [2]						
- Sample mean (SE)		XX.X (XX.XX)	XX.X (XX.XX)	XX.X (XX.XX)	XX.X (XX.XX)	XX.X (XX.XX)
- LS-mean (SE)		XX.X (XX.XX)	XX.X (XX.XX)	XX.X (XX.XX)	XX.X (XX.XX)	XX.X (XX.XX)
- LS-mean difference (SE)			XX.X (XX.XX)	XX.X (XX.XX)	XX.X (XX.XX)	XX.X (XX.XX)
- 95% CI of the difference			XXX.X, XXX.X	XXX.X, XXX.X	XXX.X, XXX.X	XXX.X, XXX.X
- Uncorrected p-value			X.XXXX	X.XXXX	X.XXXX	X.XXXX
- Corrected p-value			X.XXXX	X.XXXX	X.XXXX	X.XXXX

[1] Type III overall p-values from an ANCOVA model on the change from baseline per time point, with factors treatment, baseline value, region and previous use of biologics.  
[2] Pairwise comparisons of each group versus the placebo group (derived as contrasts within the same overall model): difference in LS-means (GLPG0634 - placebo) with 95% confidence interval of this difference, uncorrected p-value and Hommel-corrected p-value.

The table will show:

- LOCF
- observed-case

**Table PD 5: Exploratory pairwise comparisons between regimens within each daily dose level**

ANCOVA model on the change from baseline at each time point. Factors in the model are: baseline value, regimen, dose, regimen\*dose interaction, region, and previous use of biologics. Placebo subjects will not be used in this model (as there is no q.d./b.i.d. regimen available for placebo). The regimen\*dose interaction will be removed from the final model when not significant at level 0.10 (two-sided type-III p-value). Regimen will have 2 categories: q.d. or b.i.d. Dose will have 2 categories, corresponding to the total daily dose: 100 mg/day or 200 mg/day.

Per time point, the table will present:

- Per dose: difference in LS-means of q.d. versus b.i.d. within the same dose level (100 or 200 mg/day), together with a 95% confidence interval of this difference.
- Per group: p-value for pairwise comparison of q.d. versus b.i.d. These p-values will be presented both as uncorrected p-values, and are derived as contrasts within the overall model. As this is a purely exploratory analysis, no adjustment for multiplicity will be performed.

Mock:

GLPG0634-CL-203 (DARWIN1)

SAS date and time  
Page X of Y

Table PD 5: Exploratory pairwise comparisons between regimens within each daily dose level (LOCF)

Add-on therapy to methotrexate. Population: PD. Imputation method: LOCF (last observation carried forward)  
Parameter: PD marker (pg/mL)

Week	Statistic	Overall	GLPG0634 100 mg/day	GLPG0634 200 mg/day
Week 4 LOCF	Overall model p-values: [1]			
	- Baseline value	X.XXXXX		
	- Dose	X.XXXXX		
	- Regimen	X.XXXXX		
	- Dose*regimen	X.XXXXX		
	- Region	X.XXXXX		
	- Previous biologics	X.XXXXX		
	Pairwise comparisons of q.d. versus b.i.d.: [2]			
	- LS-mean difference (SE) [3]		XX.X (XX.XX)	XX.X (XX.XX)
	- 95% CI of the difference		XXX.X,XXX.X	XXX.X,XXX.X
- Uncorrected p-value		X.XXXXX	X.XXXXX	
Week 12 LOCF	Overall model p-values: [1]			
	- Baseline value	X.XXXXX		
	- Dose	X.XXXXX		
	- Regimen	X.XXXXX		
	- Dose*regimen	X.XXXXX		
	- Region	X.XXXXX		
	- Previous biologics	X.XXXXX		
	Pairwise comparisons of q.d. versus b.i.d.: [2]			
	- LS-mean difference (SE) [3]		XX.X (XX.XX)	XX.X (XX.XX)
	- 95% CI of the difference		XXX.X,XXX.X	XXX.X,XXX.X
- Uncorrected p-value		X.XXXXX	X.XXXXX	

[1]: Type III p-values from an ANCOVA model on the change from baseline per time point, with factors baseline value, dose (100/200 mg/day excluding placebo), regimen (q.d./b.i.d.), dose\*regimen interaction, region and previous use of biologics. The dose\*regimen interaction is only kept in the model when p<0.10.  
[2]: Comparisons within the same dose level of the q.d. versus b.i.d. regimens, derived as contrast within the same overall model.  
[3]: Difference: (q.d. group) - (b.i.d. group).

The table will show:

- LOCF
- observed-case

**Figure PD 1: Mean(SE) plot of the actual values**

Mean(SE) plot over time of the actual values. Use a time-proportional horizontal axis.

Mock:

[figure not shown]
GLPGXXXX-CL-XXXX

SAS date and time  
Page X of Y

Figure 14.3.2.2: Laboratory data: Mean plots of the actual values over time

Population: Safety

Clinical chemistry: Lab test name (unit)  
Normal range: XX.X - XX.X

The plot will show:

- LOCF
- observed-case

Note that this is a generic mock plot. The “normal range” line does not apply to this PD analysis.

The following standardized colors, line types and plot symbols will be used consistently throughout the entire analysis:

Treatment group label	plot symbol	line type	color
Placebo	Dot	Full line	Black
GLPG0634 100 mg q.d.	Square	Full line	Blue
GLPG0634 200 mg q.d.	Diamond	Dotted line	Green
GLPG0634 50 mg b.i.d.	Star	Full line	Red
GLPG0634 100 mg b.i.d.	Plus	Dotted line	Orange

**Figure PD 2: Mean(SE) plot of the changes from baseline**

**Figure PD 3: Mean(SE) plot of the percent changes from baseline**

**Figure PD 4: Box plot of the actual values**

**Figure PD 5: Box plot of the changes from baseline**

**Figure PD 6: Box plot of the percent changes from baseline**

**Figure PD 7: Scatterplots of the PD markers**

Individual scatterplots for each PD marker versus the others. A separate plot per time point.

- A) Actual values
- B) Change from baseline
- C) %change from baseline

### **8.3. STEP 2: ANALYSIS OF THE BIOMARKERS, SPLIT UP FOR W12 RESPONDERS AND NON-RESPONDERS**

All parameters shown are OC only.

**Table PD 6: Descriptive statistics of the actual values, split up for Week 12 responders vs non-responders**

Repeats of the analysis of previous section, splitting up each page for Week 12 responders and non-responders on a separate page:

- A) Subjects who had ACR20 response at W12
- B) Subjects who did not have ACR20 response at W12
- C) Subjects who had ACR50 response at W12
- D) Subjects who did not have ACR50 response at W12
- E) Subjects who had DAS28 remission at W12
- F) Subjects who did not have DAS28 remission at W12
- G) Subjects who had DAS28 remission or low disease activity at W12

H) Subjects who did not have DAS28 remission or low disease activity at W12.

**Table PD 7: Descriptive statistics of the changes from baseline, split up for Week 12 responders vs non-responders**

**Table PD 8: Descriptive statistics of the percent changes from baseline, split up for Week 12 responders vs non-responders**

**Table PD 9: Summary on changes from baseline with overall p-value and p-value for Week 12 response/non-response**

ANCOVA model on the change from baseline in biomarker at each time point. Factors in the model are: treatment, baseline value of the PD marker, the response (W12 OC yes/no result), region, and previous use of biologics.

The p-value for the “response” parameter will indicate whether the average change in biomarker is different for responders vs non-responders.

Plain unformatted SAS output is acceptable.

For each of the responder/non-responder combinations of above tables.

**Figure PD 8: Mean(SE) plot of the actual values: Week 12 responders vs non-responders**

Mean(SE) plots over time of the actual values like the above, eg split over 2 panels: subjects who reached response at W12 vs subjects who did not reach response at W12 (OC). For each of the responder/non-responder combinations of above tables.

**Figure PD 9: Mean(SE) plot of the changes from baseline: Week 12 responders vs non-responders**

**Figure PD 10: Mean(SE) plot of the percent changes from baseline: Week 12 responders vs non-responders**

**Figure PD 11: Box plot of the actual values: Week 12 responders vs non-responders**

**Figure PD 12: Box plot of the changes from baseline: Week 12 responders vs non-responders**

**Figure PD 13: Box plot of the percent changes from baseline: Week 12 responders vs non-responders**

#### **8.4. STEP 3: CORRELATION OF EACH INDIVIDUAL BIOMARKER VERSUS WEEK 12 EFFICACY AND SAFETY**

All parameters are analyzed as OC only.

**Figure PD 14: Scatterplots of PD markers versus efficacy**

Scatterplots of each PD marker vs the efficacy variables. Separate plot per time point.

To depict the correlation numerically, a supporting table will be added to show the Pearson correlation coefficient at each time point and for each group. Versus binary responses (ACR20/50 and DAS28(CRP) remission and remission/LDA), a point-biserial correlation coefficient will be presented. Correlations will be flagged as: strong ( $>0.7$  in absolute value), moderate ( $>0.5$  in absolute value), or weak ( $>0.3$  in absolute value).

Efficacy variables: ACR-N, DAS28(CRP), TJC68, SJC66, TJC28, SJC28, HAQ-DI, Pain VAS, Investigator's global disease activity VAS, Subject's global disease activity VAS, FACIT-F and CRP.

- A) Actual values
- B) Change from baseline
- C) Percent changes from baseline.

#### **Figure PD 15: Scatterplots of PD markers versus safety**

Scatterplots of each PD marker vs the safety variables. Separate plot per time point.

To depict the correlation numerically, a supporting table will be added to show the Pearson correlation coefficient at each time point and for each group. Correlations will be flagged as: strong ( $>0.7$  in absolute value), moderate ( $>0.5$  in absolute value), or weak ( $>0.3$  in absolute value).

Safety variables: hemoglobin, lymphocyte absolute count and subsets (CD3, CD4, CD8, CD4/CD8 ratio, CD16 CD56, CD19), neutrophils absolute count, and platelet count.

- A) Actual values
- B) Change from baseline
- C) Percent changes from baseline.

### **8.5. STEP 4: BIOMARKERS PREDICTING THE WEEK 12 EFFICACY AND SAFETY**

All parameters are analyzed as OC only.

#### **Table PD 10: Exploratory model to assess the relation between baseline PD markers and Week 12 response**

Logistic regression model, modeling the responders.

Factors in the model are: treatment, region, previous use of biologics, and the baseline values of all the PD markers. Apply a backwards elimination process to retain only relevant parameters (significance level 0.05). Treatment must always be kept in the model.

Plain SAS procedure output is acceptable. Only the final model will be shown.

For responses:

- A) ACR20
- B) ACR50
- C) DAS28(CRP) remission
- D) DAS28(CRP) remission and low disease activity

**Table PD 11:** Exploratory model to assess the relation between the Week 4 change from baseline in PD markers and Week 12 response

**Table PD 12:** Exploratory model to assess the relation between the Week 4 %change from baseline in PD markers and Week 12 response

**Table PD 13:** Exploratory model to assess the relation between baseline PD markers and Week 12 changes from baseline in efficacy

ANCOVA model, modeling: the change from baseline in efficacy at W12.

Factors in the model are: treatment, region, previous use of biologics, baseline value (except for ACR-N parameter), and the baseline values of all the PD markers. Apply a backwards elimination process (significance level 0.05). Treatment must always be kept in the model.

Plain SAS procedure output is acceptable. Only the final model will be shown.

For efficacy parameters (Week 12 OC):

- A) ACR-N
- B) DAS28(CRP)
- C) TJC68
- D) SJC66
- E) TJC28
- F) SJC28
- G) HAQ-DI
- H) Pain VAS
- I) Investigator's global disease activity VAS
- J) Subject's global disease activity VAS
- K) FACIT-F
- L) CRP

**Table PD 14:** Exploratory model to assess the relation between the Week 4 change from baseline in PD markers and Week 12 changes from baseline in efficacy

**Table PD 15:** Exploratory model to assess the relation between the Week 4 percent change from baseline in PD markers and Week 12 changes from baseline in efficacy

**Figure PD 16:** Scatterplots of baseline PD markers versus efficacy

Scatterplots of each PD marker (baseline value) vs the efficacy variables (W12 change from baseline).

Efficacy variables: ACR-N, DAS28(CRP), TJC68, SJC66, TJC28, SJC28, HAQ-DI, Pain VAS, Investigator's global disease activity VAS, Subject's global disease activity VAS, FACIT-F and CRP.

**Figure PD 17:** Scatterplots of Week 4 change from baseline PD markers versus efficacy

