## 1. INTRODUCTION

This document is an addendum to the main study SAP version 5.00. It is intended to define the statistical analysis of the additional pharmacodynamics measurements.

This Addendum to the final SAP was written after database unblinding and after viewing the main study results.

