### 3.2. TREATMENT GROUP LABELS

The following treatment group labels will be used in the tables, listings and figures:

- Placebo
- GLPG0634 100 mg q.d.
- GLPG0634 200 mg q.d.
- GLPG0634 50 mg b.i.d.
- GLPG0634 100 mg b.i.d.

The 50 mg q.d. and 25 mg b.i.d. groups will not be used (because PD samples are not analysed).

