### Notes:

- (1) The actual baseline reference value will be determined per parameter as the last available pre-dosing data point, so might differ from this “baseline” visit interval. There will be only one baseline time point in this study: the last non-missing value prior to first dosing of study drug.
- (2) Visits falling really late in the study (relative day > 182; excluding the follow-up visit) will be allocated to a “>Week 24” interval, and will not be shown in tables nor figures, but will only be listed.
- (3) For the screening and follow-up visits, no time window is defined. The visit as recorded in the eCRF will be used. Follow-up visits of subjects who discontinue the study prior to the Week 12 re-randomization will be shown separately as well in the tables that present the first part of the study only. For tables that present the study as a whole, all follow-up visits will be shown.

Tables, figures and listings will present the time points, not the visits.

For this additional PD analysis, only Baseline, Week 4 and Week 12 samples will be analyzed. These will be placed into the above time windows to allow a matching with the main analysis. If a PD result ends up in an analysis visit different from “baseline”, “week 4” and “week 12”, then it will not be used in the tables and figures.

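### The exploratory biomarker addendum corrects only across four dose contrasts and shows only final backward-elimination models; under a global null, one or two false drug-effect families and about 70 to 108 retained marker terms are expected

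*SAP*

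**What the plan says.** The addendum to the SAP is open about its timing: "This Addendum to the final SAP was written after database unblinding and after viewing the main study results" (Addendum section 1). Section 7.2 adds that everything in it is post-lock.

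- **Markers.** Section 8.1 begins "The raw PD markers will be provided by the bioanalysis lab" and lists 18 cytokines and chemokines.
- **Groups and visits.** "The 50 mg q.d. and 25 mg b.i.d. groups will not be used" (section 3.2), which leaves placebo and four active groups. Of the scheduled samples, "only Baseline, Week 4 and Week 12 samples will be analyzed" (notes to section 4.2), so there are two post-baseline time points.
- **Correction.** "Pairwise comparisons versus placebo will be presented, corrected for multiplicity using" Hommel's method (section 7.1). Table PD 4 sets this out per time point and per marker: "Per group: p-value for pairwise comparison versus the placebo group, derived from contrasts within the overall model", printed uncorrected and Hommel-corrected. No adjustment across markers, time points or outcomes is stated.
- **Responder tests.** Table PD 9 tests response against non-response in each marker's change, for four responder definitions, without correction.
- **Prediction models (Step 4, section 8.5).** Tables PD 10 to 18 put all 18 markers into each model, with treatment forced in. The rule is "Apply a backwards elimination process to retain only relevant parameters (significance level 0.05", and on reporting, "Only the final model will be shown".

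The titles of PD 5 and PD 10 to 18 contain the word exploratory. The titles of PD 4 and PD 9 do not.

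**The concern.** The addendum is meant to identify markers that the drug moves and markers that predict Week 12 outcome. Both tasks are searches over many candidates, and the planned output shows little of the size of the search. PD 4 prints a p-value headed as corrected, but the correction covers four contrasts out of a much larger set. Step 4 prints only the markers that survived elimination, with p-values computed as if the surviving model had been fixed in advance. A reader of the final models sees neither the coefficients of the dropped markers nor how close the choice was. What is at stake is which markers are carried forward as being of interest. The ACR20 result, the other efficacy analyses and the safety analyses are not touched.

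**Working it through.** The addendum states no error rate, so there is no planned figure to reproduce. All results below assume that every marker is null.

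**Counts**
- Markers: 18 (Addendum 8.1). Time points: 2. Active groups: 4.
- PD 4 families (one marker, one time point, four contrasts): 18 × 2 = 36.
- PD 9 tests: 18 markers × 2 time points × 4 responder definitions = 144.
- Step 4 models: 4 binary responses, 12 efficacy variables and 10 safety variables, each with 3 marker forms (baseline, Week 4 change, Week 4 percent change): 3 × (4 + 12 + 10) = 78.
- Step 4 marker terms: 78 × 18 = 1,404.

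PD 4 is shown for both LOCF and observed case. These nearly duplicate each other and are counted once.

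**Step 1, PD 4**
- At a nominal 5% per family: 36 × 0.05 = 1.8 expected false families. If families are independent, the chance of at least one is 1 − 0.95^36 = 84%.
- Hommel is slightly conservative here because the four contrasts share one placebo arm. Simulating four equal-sized groups against a common placebo (20,000 runs) gives 4.33% per family: 36 × 0.0433 = 1.6 expected, and 1 − (1 − 0.0433)^36 = 80%.
- The expected counts do not need independence. The 80 to 84% does, and positive correlation between markers or visits would lower it.

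**Step 2, PD 9**
- 144 × 0.05 = 7.2 expected false positives.

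**Step 4, PD 10 to 18**
- Simple figure: 18 × 0.05 = 0.9 null markers kept per model; 1,404 × 0.05 = 70 terms in all; 1 − 0.95^18 = 60% of models keep at least one, or 78 × 0.60 ≈ 47 models.
- Simulated backward elimination at 0.05: linear model, treatment forced in, region, prior biologics and baseline value eligible for removal, 18 null markers, 1,500 runs per row. The planned size is 5 × 85 = 425 subjects (Protocol 8.8.2). 340 is 80% of that, assumed to allow for missing PD results. With normally distributed markers:

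| Subjects | Marker correlation | Null markers kept per model | Models keeping at least one | Terms kept over 78 models |
|---|---|---|---|---|
| 425 | 0 | 0.93 | 59% | 72 |
| 425 | 0.3 | 1.07 | 63% | 84 |
| 425 | 0.6 | 1.38 | 70% | 108 |
| 340 | 0 | 0.98 | 61% | 76 |
| 340 | 0.3 | 1.11 | 63% | 86 |
| 340 | 0.6 | 1.32 | 67% | 103 |

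Lognormal markers gave 0.94 to 1.28 per model, 60 to 64% of models, and 74 to 100 terms. The simple figure of 70 is therefore at the low end.

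**The case against.** The strongest reply is that the documents already treat this work as exploratory. Protocol 8.8.1.7 describes PD comparisons between groups as exploratory, main SAP 6.1.5 keeps further PD analyses out of the study report, and the addendum discloses its timing. No endpoint or decision rule hangs on it. This stands, and it is why the point is minor.

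Three further replies also stand in part.

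- **PD 4 is transparent about its method.** It prints both p-values side by side, and a footnote says that each group is compared with placebo and Hommel-corrected. Every marker and time point is tabulated, so a reader could apply a wider adjustment. Neither the table nor the footnote says that the correction stops at one marker and one time point.
- **Unselected output exists.** Steps 1 to 3 give descriptives, ANCOVA results, responder splits and correlations for all 18 markers, and Figures PD 16 to 21 plot them against outcome. A reader might infer that the addendum cannot separate biology from noise at all. That goes too far, because a retained marker can be checked against these displays. They do not show what was eliminated or how.
- **The Step 4 count is easily misread.** About 70 or more retained terms are not 70 markers, since only 18 exist. The 78 models overlap heavily: DAS28(CRP) contains joint counts, CRP and patient global assessment, and each outcome is refitted with three forms of the same markers. Overlap reduces the number of distinct markers retained but not the expected number of retentions.

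The exploratory label does not answer the reporting point. The main SAP's own exploratory stepwise models (Tables 14.2.1.1.11 and 14.2.1.4.8) also tabulate only the final model, but they require an appendix that documents how the model was built. The addendum carries no such requirement.

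**Conclusion.** The point holds as a low-cost improvement to an exploratory, post-lock addendum.

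The two halves differ in size. For prediction, the plan would keep many null terms if nothing were predictive: about 70 to 108 over 78 models, with about 60 to 70% of models showing at least one. For drug effects, a reader might infer that many null markers would be reported as moved by treatment. The figures do not support that: one or two of 36 families is the expectation, so at least one is likely but many is not. PD 9 lies between, with about 7 of 144.

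The figures rest on a global null. That is a worst case, since Protocol 6.2 and 6.5 link IL-6 to JAK signalling and RA. They also rest on marker correlation between 0 and 0.6, on 340 to 425 subjects, and on the 12 logistic models behaving like the linear ones. The simulation does not reproduce the pile-up of values at 0.1 that Addendum 5.3 creates for results below the detection limit.

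**What to change.** **PD 4.** Add Benjamini-Hochberg q-values across all 36 marker-by-time overall treatment tests, which the table already produces, separately for LOCF and observed case. State in a footnote that the Hommel correction covers only the four contrasts for one marker at one time point. Label the table exploratory.

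**PD 9.** Add Benjamini-Hochberg q-values across its 144 response tests, and label it exploratory.

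**PD 10 to 18.** Show the full 18-marker model and every elimination step, in line with the appendix that the main SAP requires for Tables 14.2.1.1.11 and 14.2.1.4.8. State the number of terms tested (18 per model, 1,404 in all). Label p-values in the retained models as post-selection. Bootstrap selection frequencies would be informative but are optional.

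The cost is a little more programming and fewer markers called of interest. No new data are needed, and no other analysis changes.
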